03	10/29/2021	Revised randomization method: covariate constrained randomization instead of matched pair	Allows balance on a greater number of cluster characteristics than matched pair, allows an odd number of clusters.
03	10/29/2021	Self-report data collection will use telephone surveys at all timepoints, not just baseline. There will be no web-based survey collection.	Changed to keep mode consistent, avoid potential mode differences
03	10/29/2021	Revised consent procedures: addition of signed e- or paper consent for participation in the trial	Signed consent required by our Institutional Review Board
04	07/01/2022	Change from cluster to individual randomization	Changes in health care delivery system now allow individual randomization. Individual randomization yields more assurance of comparable balance between study arms and higher likelihood of balanced sample size by arm
04	07/01/2022	Revised inclusion: expand age from >50 to >18	Expands sample to help meet enrollment targets
04	07/01/2022	Expanded recruitment pool to include individuals with type 2 diabetes with current prescription for insulin regardless of Karter risk stratification	Expands screening to help meet enrollment targets. No change to requirement for severe hypoglycemia in past 12 months or current impaired awareness of hypoglycemia.
04	07/01/2022	Update to Study Team: replacement [name] with [name]	Administrative change: [name] has left Kaiser Permanente Washington
05	11/29/2023	Addition of new secondary outcomes of glycemic control	New outcomes consistent with International Consensus on Use of Continuous Glucose Monitoring. Will be important to assess potential

		from Continuous Glucose Monitoring (CGM) data	intervention effects on frequency of high blood sugars and variability of blood glucose levels
05	11/29/2023	Revised plan for mediation analysis	Revised mediation analysis to reflect an updated approach using the causal mediation framework instead of the Baron and Kenney framework
05	11/29/2023	Revised analysis plan for handling missing data	Lowered the threshold for attrition that would trigger use of missing data methods to account for possible selection bias (from 15% to 10%). Other editorial changes to analysis plan were made for clarity, but were not substantive.
06	11/27/2024	Clarified clustering level for analysis	Revised analysis plan to account for patient clustering in the intervention arm within group training session cohorts rather than within clinic.

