To determine if proactive care management plus MyHC-T2D is superior to proactive care management alone at preventing self-reported severe hypoglycemia in adults with type 2 diabetes at high risk for severe hypoglycemia. The primary outcome will be assessed through self-report via study survey at 14-months post baseline.

1b.2 Secondary objectives

1b.2.a Key secondary objectives

Key secondary outcomes will be assessed at 14-months post baseline through self-report in study survey (SR), continuous glucose monitors (CGMs; study participants will wear CGMs for 10 days), and electronic health records (EHRs).

1. To determine if proactive care management plus MyHC-T2D is superior to proactive care management alone in adults at high risk for severe hypoglycemia for the following:
 - Reducing percentage time with biochemical hypoglycemia (CGM assessed)
 - Reducing biochemical hypoglycemic events (CGM assessed)
 - Reducing the frequency of high blood sugars and reducing variability of blood glucose levels (CGM assessed)
 - Reducing number of severe hypoglycemic events in prior 4 months (SR assessed)
 - Reducing hypoglycemia unawareness (SR assessed)
 - Reducing number of self-reported moderate hypoglycemic events (SR assessed)

- Reducing fear of hypoglycemia (SR assessed)
- Reducing frequency of nocturnal hypoglycemia (SR assessed)
- Improving diabetes and hypoglycemia knowledge (SR assessed)
- Improving diabetes self-efficacy (SR assessed)
- Reducing hypoglycemia related healthcare utilization, including urgent care, Emergency Department and inpatient visits related to hypoglycemia (EHR assessed)

2. To assess differences in glycemic control, indicated by Hemoglobin A1c, between study participants in the proactive care management plus MyHC-T2D group and the proactive care management alone group.

1b.2.b Other secondary Objectives

Conduct a mixed methods process evaluation to evaluate the fidelity of implementation of intervention components, and clarify the causal pathway if intervention effects are found.

1c. Trial design

This study is an individually randomized controlled trial (RCT) comparing proactive care management^{30,31} to proactive care management plus MyHC-T2D.^{25,32}

2. Methods: Participants, interventions and outcomes

2a. Study setting

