Fidelity	Is the intended intervention delivered at the cluster level? individual level?	Qualitative analysis of nurse and patient interviews, nurse observations -Quantitative analysis of fidelity checklists and participant contacts
Dose	Is the intended amount of the intervention delivered at the cluster level? Individual level?	-Qualitative analysis of nurse and patient interviews, nurse observations -Quantitative analysis of fidelity - checklists and participant contacts
Mechanism	Why and how did the intervention work?	-Quantitative mediation analysis of causal pathway -Qualitative analysis of patient and nurse interviews
Reach	Did the intended populations receive the intervention?	Quantitative descriptive analysis of clusters and individuals using administrative and EHR data
Context	What clinic, institutional, state and national factors may moderate intervention?	-Qualitative analysis of interviews with stakeholders

- **Telephone surveys** will be administered by the KPHRI SRP. Staff will be trained and quality monitored as described in Section 2.c.1, Data Collection Methods, Self-Report data, above. Instruments will be programmed with skip patterns and range checks. KPHRI, and specifically SRP, maintain a HIPAA-compliant environment. Data in DatStat Illume, which will be used for survey data, is encrypted at all times. Other protections include real-time scanning for viruses and malware, and scanning and blacklisting of suspicious incoming email and web traffic. Multiple real-time systems monitor internal activity including movement of data between internal systems. Data collected through DatStat Illume are stored on Microsoft SQL Server systems located behind the Kaiser Permanente firewall. Access to both the DatStat web server and the database servers is restricted to IT Operations staff. Access to data collected through DatStat is limited to Kaiser Permanente Washington employees with a need for access.
- **Data collected via CGM:** Study staff will download data from each participant's CGM sensor transmitter unit using the Dexcom receiver. The receiver will transmit this data to the Dexcom CLARITY server from which data and reports will be retrieved. Data for individuals will be identified only by a device ID, which will be linked to study ID using crosswalks kept only at KPHRI.

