Process Evaluation: We will use descriptive analysis to assess intervention recruitment, reach and delivery. If significant differences ($p<0.05$) between intervention groups are found for the primary outcome, we will perform mediation analysis to test the hypothesis that the possible causal pathway for reducing the occurrence of severe hypoglycemia is through improvements in hypoglycemia knowledge, hypoglycemia awareness, self-efficacy of hypoglycemia management, blood glucose testing, and hypoglycemic medication adjustment and other factors in causal pathway in **Figure 2**. Mediation analysis will use a regression-based approach within the causal mediation framework,⁵³ separating the total intervention effect into a natural indirect effect (effect occurring through the mediator), and a natural direct effect (effect through all other pathways). To estimate these effects, we will use either a log-linear or Poisson model for the outcome model (depending on whether the primary outcome is defined as a binary or count variable), and linear regression for the mediator model. The effect of each mediator will be estimated in separate models.

4d. Trial monitoring

4d.1 Data monitoring

This study will have a Data Safety Monitoring Board (DSMB) to ensure safety of research participants. The DSMB will include an external researcher with prior DSMB experience (the chair), and two clinicians with expertise in type 2 diabetes and in the treatment and care for patients with severe hypoglycemia and impaired hypoglycemia awareness. The DSMB will meet once in the first 6 months after study funding and prior to patient enrollment to review study protocols and plans for study reports (enrollment, completion, and adverse event-reporting tables by study group) and recommend changes. The study team will track participant-reported serious adverse events whether related or not to study participation. The team will provide ongoing reports to the DSMB and the Institutional Review Board. The DSMB will meet twice per year, in person or by phone, as directed by the committee. The study Principal Investigator, biostatisticians, and project manager will attend all open portions of DSMB meetings.

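### Mediation analysis is made conditional on p<0.05 for the primary outcome, although the planned natural direct and indirect effects do not need that condition; estimate them in every case, as exploratory

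*Combined protocol and SAP*

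**What the plan says.** Section 4c, Process Evaluation, opens the mediation plan with a condition: "If significant differences ($p<0.05$) between intervention groups are found for the primary outcome, we will perform mediation analysis". It then specifies the method: "Mediation analysis will use a regression-based approach within the causal mediation framework", "separating the total intervention effect into a natural indirect effect (effect occurring through the mediator), and a natural direct effect". For estimation, "we will use either a log-linear or Poisson model for the outcome model", with a linear model for the mediator and each mediator handled separately. Nothing is said about what happens to this analysis if the condition fails.

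Two other places describe the same work more loosely. Objective 1b.2.b is to "clarify the causal pathway if intervention effects are found"; it gives no p-value and does not single out the primary outcome. Table 1 asks, under Mechanism, "Why and how did the intervention work", and lists mediation analysis beside "Qualitative analysis of patient and nurse interviews", with no condition on either.

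The Protocol Amendment History for version 05 gives this rationale for the mediation change: "Revised mediation analysis to reflect an updated approach using the causal mediation framework instead of the Baron and Kenney framework". It does not mention the p<0.05 condition.

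**The concern.** A significant total effect is the first step of the Baron-Kenny procedure. Natural direct and indirect effects do not need it. They can be estimated when the total effect misses significance, and also when the two components have opposite signs and largely cancel.

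Two things are at stake.

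- **Loss.** After a near miss on severe hypoglycemia, the plan gives no estimate of how much of any effect ran through awareness, knowledge or the other hypothesised mediators, although the data needed have been collected.
- **Selection.** If the split is reported only after p<0.05, it is reported only from samples whose total effect is, on average, too large. That excess has to go into one of the two components.

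**Working it through.** **Inputs.** From section 2f: 102 analysed per arm, control risk 60%, type I error 0.05 (taken as two-sided), 90% power for 22.6 points and 80% power for 19.7 points, and a 30% reduction called meaningful (read as relative, so 60% to 42%, 18 points). The 15-point row is an added illustration.

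**Step 1: reproduce the plan's power.** Power = Φ[(d − 1.96·se0)/se1], with se0 = √[2·p̄(1−p̄)/n] and se1 = √[(p0(1−p0)+p1(1−p1))/n].

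- d = 0.226: se0 = 0.0700, se1 = 0.0682, so Φ(1.30) = 0.904 (stated 90%).
- d = 0.197: se0 = 0.0700, se1 = 0.0686, so Φ(0.87) = 0.808 (stated 80%).

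Both figures reproduce. Power is also the chance that the mediation analysis is run.

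**Step 2: how often the condition fails, and how far significant results overshoot.** Exact binomial enumeration of the pooled two-proportion z-test, 102 per arm:

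| True difference | MyHC-T2D risk | p<0.05 | Condition fails | Mean difference given p<0.05 | Ratio to truth |
|---|---|---|---|---|---|
| 22.6 points | 37.4% | 91% | 9% | 23.8 points | 1.05 |
| 19.7 points | 40.3% | 83% | 17% | 21.8 points | 1.11 |
| 18 points | 42% | 76% | 24% | 20.9 points | 1.16 |
| 15 points | 45% | 60% | 40% | 19.4 points | 1.30 |

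The Step 1 formula gives slightly higher failure rates: 10%, 19%, 27% and 43%.

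**Step 3: is a pathway visible in the failing trials?** Simulated trials with 102 per arm, log-linear outcome model, linear mediator model, no mediator-outcome confounding and no clustering. The pathway counts as shown when the arm-to-mediator and mediator-to-outcome coefficients are both significant. Mediator strength is an assumption throughout.

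- Slope −0.3 log-risk per SD, half of the effect mediated: shown in 99% of failing trials at RR 0.623, 97% at RR 0.70, 70% at RR 0.80 and 21% at RR 0.90.
- RR 0.70, fully mediated: nearly 100%.
- RR 0.70, mediator shifted by only 0.3 SD: about 42% if the indirect effect is RR 0.94, and about 19% if it is RR 0.97.
- Opposing effects (indirect −0.15, direct +0.15 on the log scale, no total effect): 90% of all trials both fail the condition and show the pathway.

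These simulations test the log relative risk with a robust Wald test, which passes less often than the z-test in Step 2 (68% against 76% at RR 0.70). At 42% versus 60%, the log-RR standard error is √[0.58/(102·0.42) + 0.40/(102·0.60)] = 0.142, and Φ(0.357/0.142 − 1.96) = 0.71. Capping simulated risks at 0.99 takes off a little more.

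**Step 4: where the overshoot goes.** Mean log RR over all trials, then over trials with p<0.05 (proportion = indirect/total):

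| Scenario | Direct, all → p<0.05 | Indirect, all → p<0.05 | Proportion mediated, all → p<0.05 |
|---|---|---|---|
| RR 0.623, half mediated | −0.241 → −0.273 | −0.231 → −0.233 | 0.231/0.473 = 49% → 0.233/0.505 = 46% |
| RR 0.70, half mediated | −0.180 → −0.250 | −0.174 → −0.177 | 0.174/0.353 = 49% → 0.177/0.427 = 41% |
| RR 0.70, fully mediated | −0.004 → −0.073 | −0.348 → −0.350 | 0.348/0.352 = 99% → 0.350/0.422 = 83% |
| RR 0.70, true direct effect +0.10 | +0.093 → +0.022 | −0.444 → −0.446 | not a share (exceeds 100%) |

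The indirect effect hardly moves. The direct effect is pushed in the direction of the observed total effect.

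**The case against.** The case for leaving the text alone has real force.

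- **Explaining an effect presupposes one.** Objective 1b.2.b is itself conditional, and Table 1 asks how the intervention worked. Section 4c can be read as making that condition concrete for the outcome being mediated. A reader might infer that the condition was left over by oversight from the Baron-Kenny plan. The documents do not show that: the amendment entry is silent on it, and the objective carries a similar condition. What stands is that section 4c is narrower than the objective and that the estimands do not need it.
- **Much of the mechanism evidence is unconditional.** A reader might infer that a near miss leaves no quantitative answer on mechanism. That goes too far. Awareness, knowledge and self-efficacy are secondary outcomes (section 2d.2) modelled by arm at each follow-up (section 4c), and the interviews and the fidelity and dose work go ahead regardless. What is lost is the direct/indirect split, plus arm effects on glucose testing and medication adjustment, which are not listed as secondary outcomes.
- **Dropping the condition does not cure selection.** If this trial reaches p<0.05, the direct effect computed is the same number either way. Nor is the distortion always away from no effect: an opposing direct effect moves toward null, as the last row of Step 4 shows. Both points are accepted in full.
- **Multiplicity.** The condition limits unadjusted testing of five or more mediators after a null result. Intervals and an exploratory label answer this adequately.

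**Conclusion.** The point holds as an inexpensive improvement to a secondary analysis. The p<0.05 condition is unnecessary for the planned estimands and would remove the direct/indirect split in about 9% of trials at the 90%-power effect, 17% at the 80%-power effect, 24% at a 30% relative reduction and 40% at 15 points. Across plausible but assumed mediator strengths, roughly 40% to nearly 100% of those trials would show a significant indirect effect; a very weak mediator or a total effect near null gives less.

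Selection is a separate matter of interpretation. The total effect is overstated by about 5% at 22.6 points and 16% at 18 points among significant trials, nearly all of it assigned to the direct effect, so a proportion mediated reported after significance tends to be too low. It would be wrong to conclude that the primary comparison or its type I error is affected.

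The failure rates assume an unadjusted test, a 60% control risk and 80% response. Covariate adjustment and clustering by training cohort would shift them somewhat.

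**What to change.** In section 4c, Process Evaluation, replace the opening condition with: *Whatever the p-value for the primary outcome, natural indirect and direct effects for each mediator will be estimated with 95% confidence intervals and labelled exploratory.* Align the conditional wording of objective 1b.2.b.

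Add two reporting rules. First, give no proportion mediated when the confidence interval for the total effect includes no effect. This keeps a significance condition for that one ratio, deliberately, because its denominator is then close to zero. Second, state beside any proportion reported after a significant primary result that it tends to understate mediation.

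The cost is a few sentences and a modest amount of analysis on data already being collected. The downside is that the estimates will be imprecise and only exploratory when the total effect is near null.

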Participation in this study is voluntary. Even after consent, participants may choose to not do specific study components such as CGM data collection. They may decline survey questions or choose not to participate in intervention activities. Participants will not be considered withdrawn from the study unless they state clearly that they wish to withdraw. For participants who do not complete specific activities but do not withdraw consent, we will continue to use what information they have provided and will extract and use EHR data as described in the consent process. If participants withdraw their consent, we may still use information collected before withdrawal, but will not collect any additional information and will destroy any record of their name or other information that may identify them. This will be clearly stated in the consent materials and reviewed as part of the informed consent process.

4a.6. Process evaluation

In addition to collection of data for primary and secondary outcomes described above, we will conduct a process evaluation to assess whether the interventions were implemented as planned and to test and refine the hypothesized causal pathways (Figure 5). These results will be essential to ensure future implementations of severe hypoglycemia prevention are centered on patient needs and are feasible and acceptable for healthcare providers and systems.

We will use qualitative and quantitative methods for assessing the *fidelity, dose and mechanism* of the intervention.

Qualitative assessments: To assess delivery *fidelity* and *dose* to clusters and individuals, we will observe nurse care managers and diabetes nurse educators working with participants and interview them after interventions.⁵⁷ For observations of nurse care managers, we will develop a tool to capture information on protocol integrity for outreach calls to patients in both comparator groups. We will do observations in the last 2 months of intervention implementation to separate evaluation from earlier fidelity monitoring and feedback training to nurses conducted by the intervention team. We will observe nurses on initial proactive care management outreach calls in each comparator group. We will observe nurses on the two follow-up educational calls in the MyHC-T2D group. We will also observe selected MyHC-T2D group educational sessions facilitated by the diabetes nurse educators.

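### Modelling each mediator on its own can bias the natural indirect effect of a downstream mediator; a joint analysis of the mediator set should be added

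*Combined protocol and SAP*

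**What the plan says.** The Process Evaluation paragraph of section 4c makes mediation analysis conditional on p<0.05 for the primary outcome. Its aim is to "test the hypothesis that the possible causal pathway for reducing the occurrence of severe hypoglycemia" runs through improvements in "hypoglycemia knowledge, hypoglycemia awareness, self-efficacy of hypoglycemia management, blood glucose testing, and hypoglycemic medication adjustment and other factors in causal pathway". The estimands are given as "separating the total intervention effect into a natural indirect effect (effect occurring through the mediator), and a natural direct effect". For estimation, "we will use either a log-linear or Poisson model for the outcome model", with linear regression for the mediator, and then: "The effect of each mediator will be estimated in separate models".

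The readable text gives no causal order among the mediators, no list of mediator-outcome confounders, no joint model, no sensitivity analysis and no rule for reading the separate results together. Section 4a.6 says that the process evaluation will "test and refine the hypothesized causal pathways" and refers to a figure that is not reproduced in the text available here. Table 1 assigns the question of why and how the intervention worked to this mediation analysis together with patient and nurse interviews.

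Three other sections bear on how the mediators relate:
- Section 1a: impaired awareness develops through repeated exposure to low glucose.
- Section 2d.1: warning symptoms come back once low glucose has been avoided for three to four weeks.
- Section 2c.1: impaired awareness is one of the reasons for nurses and primary care providers to consider reducing glucose-lowering medication and increasing self-monitoring.

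**The concern.** By this account, medication adjustment or glucose testing that reduces hypoglycemia also restores awareness, and impaired awareness in turn leads to medication change and testing. Medication adjustment can plausibly lower severe hypoglycemia without passing through awareness. If the intervention changes it, as the plan hypothesizes, it confounds the relation between awareness and the outcome and is itself a consequence of arm.

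In that structure the natural indirect effect of the later mediator is not identified without further parametric assumptions. A regression on arm and that mediator alone also credits it with part of the earlier mediator's effect.

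At stake is the mechanism conclusion. Section 4a.6 regards the process results as essential for later implementation, so a component that merely travels with an effective one could be reported as a reason the intervention worked.

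**Working it through.** **The plan's own figure.** The documents give no number for the mediation analysis. The nearest is the primary-outcome assumption in section 2f: 60% versus 37.4% with 102 per arm, stated as 90% power.
- Mean proportion 0.487; pooled SE = √(2 × 0.487 × 0.513 / 102) = 0.0700.
- Unpooled SE = √((0.60 × 0.40 + 0.374 × 0.626) / 102) = 0.0682.
- z = (0.226 − 1.96 × 0.0700) / 0.0682 = 1.30, so power is 90.4%. The stated figure reproduces (two-sided, no continuity correction).
- The implied total effect is ln(0.374/0.60) = −0.473. It only sets the scale and cancels from the shares below.

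**Assumed model (none of these path strengths is in the documents).** Arm A shifts M1 by a = 0.8 SD. M2 = d × M1 + error, with d = 0.8. Residual variances are 1. The outcome has a log-linear mean with coefficients b1 and b2 for M1 and M2, and no interaction. The two mediators together carry 60% of the total effect.

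**Formula.** With M2 and arm alone in the outcome model, the coefficient of M2 is b2 + b1 × d/(d² + 1). Multiplying by the arm effect on M2, which is a × d:
- separate-model indirect effect of M2 = a × d × b2 + (a × b1) × d²/(d² + 1).

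The first term is the true indirect effect of M2. The second is bias: the part of the effect that M1 carries by other routes, multiplied by d²/(d² + 1). At d = 0.8 this factor is 0.64/1.64 = 0.390.

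**Results when M1 affects the outcome by another route.**
- M1 carries 30% outside M2, and M2 truly carries 30%: 30% + 30% × 0.390 = 41.7%.
- M2 follows M1 but does not affect the outcome, and M1 carries 60%: 0% + 60% × 0.390 = 23.4%.

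A Poisson simulation of 300,000 participants with these coefficients gave 41.8% and 23.2%.

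**Range over d, true shares held fixed (assumed values).**
- d = 0.4: factor 0.16/1.16 = 0.138, giving 34.1% against 30% and 8.3% against 0%.
- d = 1.2: factor 1.44/2.44 = 0.590, giving 47.7% against 30% and 35.4% against 0%.

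**All settings side by side (share of the total effect).**

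| Structure | True M1, M2 | Separate models M1, M2 |
|---|---|---|
| Pure chain, M1 to M2 to outcome | 60%, 60% | 60%, 60% |
| Chain, M1 also acts on outcome | 60%, 30% | 60%, 41.7% |
| M2 follows M1, no effect on outcome | 60%, 0% | 60%, 23.4% |
| Parallel, independent residuals | 30%, 30% | 30%, 30% |
| Parallel, residual correlation 0.3 | 30%, 30% | 39%, 39% |
| Parallel, residual correlation 0.5 | 30%, 30% | 45%, 45% |
| Parallel, residual correlation 0.7 | 30%, 30% | 51%, 51% |

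In the parallel rows each separate share is 30% × (1 + r). In every row a correctly specified outcome model with both mediators returns the joint 60%, because a × b1 plus the arm effect on M2 times b2 is 60% by construction.

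**The case against.** The strongest reply is that separate models are not wrong in themselves. A reader might infer that natural effects are never identified when mediators are modelled one at a time. The table shows otherwise: the first mediator in an order, each link of a pure chain, and mediators that are independent given arm are all estimated correctly. If the mediators were purely links of one chain, a full share for each would be the right answer. This stands, and it limits the point to mediators that share causes with, or lie downstream of, another mediator that has its own route to the outcome.

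A reader might also infer that the plan counts the same effect several times. The documents do not support that as an error in the plan. Each model sets one mediator against a "natural direct effect (effect through all other pathways", which by definition includes routes through the other mediators. Nothing says that the separate shares will be added or ranked. Non-additivity misleads only if they are read as shares of one whole. The bias calculated above, however, does not depend on adding: it is present in a single result read alone.

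Three further replies have some force. The pathway figure cannot be seen, so an intended order may exist; but the model rule in section 4c does not use one. Interviews also inform the mechanism question, which softens the consequence. And a joint model still assumes no unmeasured mediator-outcome confounding, including by the unspecified other factors.

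**Conclusion.** The point holds in a limited form. Given the dependence that sections 1a, 2c.1 and 2d.1 describe, the separate-model rule can overstate a downstream mediator: 41.7% instead of 30%, or 23.4% for one with no effect. These sizes rest on assumed path strengths, linear Gaussian mediators and a log-linear outcome without interaction. They show that the error can be material; they do not predict this trial's result.

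The loss of nonparametric identification is confined to a later mediator confounded by an earlier, arm-affected one with another route to the outcome. The consequence is bounded: the analysis is conditional on a significant primary result, belongs to the process evaluation under other secondary objectives (section 1b.2.b), and does not touch the primary test or the sample size. It is worth correcting because the correction is cheap.

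**What to change.** In the Process Evaluation paragraph of section 4c:
- Keep the single-mediator models, labelled as descriptive.
- Add one outcome model containing all measured mediators. From it, report the joint natural indirect effect of the set and the remaining direct effect, with bootstrap intervals. This needs no assumed order among the mediators.
- Name the mediator-outcome confounders to be adjusted for, and add a sensitivity analysis for unmeasured ones.
- State that single-mediator effects are not additive and are not a decomposition of the total effect.
- Optionally, report sequential or interventional effects for each mediator. Sequential effects require the assumed order to be stated before outcome data are analysed.

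The cost is wording and some programming. No new data are needed, since section 4a.6 already plans the mediator variables from self-report and the electronic record. With about 204 participants analysed (section 2f), intervals will be wide, especially for individual mediators.
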